First, the research team at IIT partnered with three sites: (1) Heartland Alliance Health (HAH; formerly known as Heartland Health Outreach), an established non-profit organization primarily located in Chicago's Edgewater-Uptown neighborhood. HAH serves a large population of African Americans with serious mental illness; (2) ACCESS community health network serving underserved communities (30% African American) within thirty-five federally qualified health centers (FQHCs) located across Cook and DuPage counties; and (3) Trilogy, a not-for-profit behavioral health organization, primarily located in Chicago's Rogers Park neighborhood, with more than 45 years of experience of serving people with serious mental illness. HAH hosted the BHL and PHN programs during Cohort 1 of the study while Trilogy hosted them during Cohorts 2 and 3. Second, physical flyers were posted around the city of Chicago at other local clinics, non-profit organizations, churches, food pantries, and recreation centers. Third, members of the CBPR team approached individuals directly by providing details about the study and asking if they were interested in participating. Fourth, the project manager and other research staff conducted brief presentations to staff members at applicable community agencies to generate interest. Finally, study information was posted through social media accounts to recruit potential participants online. The target sample size for this study was 210 African Americans with serious mental illness and weight concerns (or 70 per condition).

Screening

Once potential participants expressed interest in the study, they were directed to complete a 5-to-10-minute screening questionnaire, conducted prior to obtaining consent for study participation. This began by either completing an abbreviated version of the screener online,

sending an email to the official research study account, or calling the screening phone line directly. If they chose one of the first two options, a member of the research staff would call them back to complete the remainder of the screening process. The screening questionnaire included questions to assess whether individuals met the inclusion criteria for the study:

- At least 18 years of age or older (no maximum cap)
- Identify as African-American
- Identify as either male or female

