IIT research staff guided all potential participants through an informed consent process prior to starting the baseline survey assessment. The informed consent included five key sections: (1) purpose of the study, (2) groups and requirements of the study, (3) risks, (4) benefits, and (5) compensation. Participants were also provided with the number for a psychologist to talk to, free of charge, to discuss any feelings related to participating in the study, or their rights as a participant.

Release of Information.

Individuals entering the study during Cohorts 2 and 3 with Trilogy were asked to sign a release of information form. The form was required so that the IIT research team could release relevant contact information to Trilogy for the purposes of informing them of the participant’s assignment to one of the intervention conditions, confirming insurance eligibility, and scheduling

an intake meeting. Participants were not allowed to begin the intervention until Trilogy staff completed their intakes and registered them as existing clients within the organization.

Study Procedures

Once individuals were determined to be fully eligible and completed all necessary documentation, they were enrolled as research participants into a designated cohort and randomized to one of three study conditions for a period of 12 months. Cohort enrollment periods appear to be longer than twelve months because participants completed their baseline in sections: Cohort 1 sections were enrolled from December 2017 through March 2019. Cohort 2 sections were enrolled from January 2019 through August 2020; and Cohort 3 sections were enrolled from December 2019 through February 2021.

Randomization.

This study utilized stratified block randomization by gender. IIT research staff picked up an envelope labeled either “female” or “male” for the participant’s identified gender, and blindly chose one of three cards at random which indicated the assigned research condition. Participants were randomized to either Integrated Care-Treatment as Usual (IC-TAU), Behaviors for Healthy Lifestyles (BHL), or Behaviors for Healthy Lifestyles plus Peer Health Navigation (BHL+PHN).

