IC-TAU Condition. Integrated care is defined as care that involves both medical and behavioral health providers in collaboration to meeting the healthcare needs of patients (Agency for Healthcare Research and Quality, n.d.). Participants randomized to this condition received integrated care services “as usual” provided by either HAH for Cohort 1 or Trilogy for Cohorts 2 and 3. Those who were not already recruited as active patients at these sites were given information on how to enroll.

BHL Condition. Participants randomized to the BHL condition were asked to attend twenty-six weekly classes followed by four review classes over the course of the first eight months of their study enrollment. Each participant received a workbook to follow along with during class. The class curriculum covered topics related to diet and exercise such as portion control, alternative meal choices, getting active, and the impact of mental health and substance use. Classes were led by a BHL class facilitator at HAH for Cohort 1 and Trilogy for Cohorts 2 and 3. Facilitators received special manualized training from IIT research staff on how to deliver the BHL program to study participants. The Cohort 1 facilitator was a trained dietitian who identified as White. The facilitator for the latter two Cohorts was an African American peer with lived experience of mental illness. Participants were also asked to attend between 1-2 weekly physical activity sessions. During these sessions, BHL facilitators led participants in different types of exercises such as yoga, Zumba, or brisk walks in the community. BHL facilitators also conducted weekly one-on-one sessions with group members outside of the class to review goals.

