Participants were able to use their workbooks to follow along with class content and guided physical activity sessions over the phone. Low-impact exercises were written out and transcribed for BHL facilitators so that they could be delivered verbally. Peer health navigation activities were also transitioned to a telephonic format and included extra guided physical activity sessions, identifying physical activity opportunities that could be conducted from home or safely in the community, meal planning, setting up grocery delivery at home, or applying for additional resources such as free ride cards and food stamps. By June 2020, peer health navigators were encouraged to meet with interested participants face-to-face under the appropriate COVID-19 safety protocols (i.e., everyone must wear face masks covering the nose and mouth, keep 6 feet of distance, and use hand sanitizer) to provide the intervention whenever possible. BHL and BHL+PHN participants continued to receive virtual punches on their cards and all gift card payments were mailed to their home addresses.

Statistical Analysis Plan

Due to missing data, data analysis plan was revised from 3x4 and 3x13 ANOVAs to 3x2 ANOVAs (treatment groups X timepoints [baseline & 8-month]) for all intent-to-treat analyses, minimizing missing data, retaining power, maintaining intended plans to observe interventions from pre-test to post-test. Post-hoc comparisons were conducted as needed. As-treated analyses were conducted through 2x2x2 ANOVAs (treatment groups [BHL & BHL+PHN] X timepoints [baseline & 8-month] X attendance [yes or no, attended at least once]). If significant findings were observed, secondary analyses incorporated 4-month (mid-test) and 12-month interviews (follow-up) to determine if any changes occurred during these timepoints.

Originally, it was also proposed that a few intervention-related variables may be included as potential covariates in the analyses. These variables included: Study site where interventions were hosted (i.e., HAH or Trilogy), method of participant compensation (i.e., raffle or punch card), and format of interventions (i.e., in-person or online). As the addition of these covariates would only allow for conservative analyses without meaningful interpretation, potential cohort effects were not examined. Still, demographics would have been included as covariates if any differences were observed across treatment groups at baseline.

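### Gender was the randomisation stratum but is left out of the 3x2 intent-to-treat model, and the baseline-difference rule would almost never bring it in; the test may be slightly conservative.

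*Combined protocol and SAP*

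**What the plan says.** Under Randomization, the protocol states: "This study utilized stratified block randomization by gender". Staff took the envelope for the participant's gender and "blindly chose one of three cards at random which indicated the assigned research condition". No other stratum is named, and the text does not say whether a drawn card went back into the envelope.

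The Statistical Analysis Plan reports a change of model: "Due to missing data, data analysis plan was revised from 3x4 and 3x13 ANOVAs to 3x2 ANOVAs". The two time points are baseline and 8 months, and gender is not a factor.

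Covariates are handled in two sentences. Site, incentive method and intervention format had been proposed, but: "As the addition of these covariates would only allow for conservative analyses without meaningful interpretation, potential cohort effects were not examined". For other variables, "demographics would have been included as covariates if any differences were observed across treatment groups at baseline". Gender is not named there. Read as a demographic, this is its only stated route into the model.

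**The concern.** A factor used to restrict the randomisation is normally carried into the analysis. If true blocks made the arms alike on gender and gender predicts change, the arm means vary less than the unadjusted residual variance implies. The arm-by-time test then rejects in fewer than 5% of null trials, and its intervals are wider than the design warrants.

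The rule for demographics works against this. Blocking is meant to prevent a gender difference between arms, so waiting to observe one excludes gender almost by construction. If the draws were independent, the rule selects gender only by chance. What is at stake is some precision, not validity.

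**Working it through.** **Inputs from the documents.** N = 210, 70 per arm (Recruitment); gender as the only named stratum (Randomization); a 3x2 model (SAP); expected standardised changes of -.07 and -.20, and 81% power (SAP, power paragraph). **Assumed:** two-sided 5% test, IC-TAU change of 0, 60:40 gender split, blocks of three within gender. The documents do not say how strongly gender predicts change, so a range is shown.

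**1. The plan's own figure.** With means 0, -.07, -.20 and SD 1, f = .083 and the noncentrality is 210 x .0829² = 1.44, which gives 17% power for a three-group F test. On a change score, 81% needs a noncentrality of 10.01. That implies a baseline-to-8-month correlation of about .928, since 1.44/[2(1 - .928)] = 10.0. No correlation is stated, so the 81% cannot be checked. It serves below only as an illustrative anchor.

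**2. Why size falls.** With two time points, the arm-by-time test is a one-way ANOVA of change. Under true blocks gender adds nothing to differences between arm means, whose variance is proportional to 1 - R2, but it stays in the residual variance. For a 2-df test, approximately:

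size = .05^(1/(1 - R2(1 - L))), where L is the share lost at random.

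**3. R2 for a given gender difference.** With d the male-female difference in SDs of change within gender, R2 = .24d²/(1 + .24d²), where .24 = .6 x .4. At d = .25, R2 = .0150/1.0150 = 1.5%. At d = .47, R2 = .0530/1.0530 = 5%.

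| d (SD) | R2 | Size, complete data | Size, 30% loss | Size, 50% loss | Interval width, 1/sqrt(1 - R2) | Power with gender added |
|---|---|---|---|---|---|---|
| .25 | 1.5% | .0478 | .0485 | .0489 | 1.007 | 81.6% |
| .47 | 5% | .0427 | .0449 | .0463 | 1.026 | 83.1% |
| .68 | 10% | .0358 | .0399 | .0427 | 1.054 | 85.1% |
| .86 | 15% | .0295 | .0352 | .0392 | 1.085 | 87.2% |

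Interval width and power are for complete data. Power is noncentrality 10.01/(1 - R2) with F(2, 206).

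Simulation (20,000 trials per cell) gave unadjusted sizes of .042/.036/.029 at R2 5/10/15% with complete data, .047/.040/.034 with 30% loss and .047/.042/.040 with 50%. The adjusted test stayed at .048-.052. With cards replaced, the unadjusted test stayed at .047-.051, so there is no deflation.

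**4. The baseline rule.** With an assumed threshold of p < .05 and 6,000 simulated trials, blocked gender was selected in 0%, 0% and 0.2% of trials at 0/30/50% loss. With cards replaced it was selected in 5.2-5.4%.

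**5. The three covariates that the SAP names.** Assume equal cohorts and code incentive and format as 0 in IC-TAU, with the Cohort 1 incentive distinguished from that of Cohorts 2-3, and only Cohort 3 online. Let p be the share of each active arm coded 1, and n the arm size. The variance of an active-versus-IC-TAU contrast is multiplied by 1 + [p²/(2n p(1 - p))]/(2/n) = 1 + p/[4(1 - p)].

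- Format, p = 1/3: 1.125, and omnibus power falls from 81% to 77%.
- Incentive, p = 2/3: 1.5, and power falls to 69%.
- Site, incentive and format together: 2.5 by least squares, and power falls to 58%.
- Site alone, with cohorts balanced across arms: the site mean does not differ between arms, so the multiplier is 1.

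The contrast of BHL+PHN with BHL is unaffected in every case.

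**The case against.** The strongest reply is that the SAP never calls covariate adjustment in general conservative. A reader might infer that it does, but the sentence concerns three named variables. Two of them, incentive and format, vary only within the active arms, and step 5 shows that adjusting for them can cost real power. That part of the reason stands. Site is different, because IC-TAU participants were also served at HAH or Trilogy. Even there, the remark about interpretation has force. "HAH hosted the BHL and PHN programs during Cohort 1 of the study while Trilogy hosted them during Cohorts 2 and 3", and facilitators changed at the same point: "The facilitator for the latter two Cohorts was an African American peer with lived experience of mental illness". Site therefore cannot be separated from cohort.

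A reader might also infer that omitting cohort is an error of the same kind. The documents do not support that. Participants were assigned to a cohort at enrolment ("they were enrolled as research participants into a designated cohort and randomized to one of three study conditions"), but cohort is not a named stratum. The case for it is precision only, and the SAP discloses that cohort effects were not examined.

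On gender, the reply is that the effect is small and in the safe direction. This is fair: R2 of 5% or more needs a gender difference in change of nearly half an SD. The conditional wording of the rule also suggests that no baseline difference was found, so removing it may change no reported result. Neither reply gives a reason to leave out the stratum.

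**Conclusion.** The point holds as a minor one about gender. The only named stratum is absent from the 3x2 model, and its only stated way in is a rule that almost never selects a blocked factor. If cards were not replaced and gender predicts change, the nominal 5% test has size about .048 at a difference of .25 SD and about .043 at .47 SD, and intervals are about 0.7% and 2.6% too wide. These figures assume complete data and a 60:40 gender split; random loss shrinks the effect. If cards were replaced, or if gender does not predict change, size is not deflated.

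A reader might infer bias, inflated type I error or altered conclusions. None follows: the arms remain randomised, the error is toward too few rejections, and the documents give no results by gender. The SAP's *conservative* label is inaccurate for site only.

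**What to change.** 1. Replace the baseline-difference rule for gender with inclusion by design, for example: *Gender was the randomisation stratum and is included in the adjusted analysis whatever its balance across arms.*
2. Beside the 3x2 result, report one sensitivity analysis that adds gender and gender-by-time, which is the change score regressed on arm and gender. Label it post hoc, because the SAP describes the analyses as already conducted. The 3x2 result stays as it is.
3. In the covariate sentence, limit the reason about conservatism to incentive and format. For site, say that it changed with cohort and cannot be separated from it.

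A line saying whether cards were replaced would tell readers which case applies. Cohort adjustment and by-cohort contrasts are optional and not part of this fix.

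The cost is wording, one degree of freedom and a re-run on data already held. If gender predicts nothing and cards were replaced, the precision lost is worth about 1/210 = 0.5% of the sample at N = 210; with intact blocks it is close to nil.

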A power analysis was carried out prior to the beginning of the study in MPLUS using the Saris and Satorra (1993) method. Based on past research, an effect size (standardized weight change) of -.07 in the BHL condition and -.20 in the BHL+PHN condition was expected. A sample size of 210 has 81% power to detect group differences. Prior to conducting any analyses, the data was assessed for missing values, normality, and skewness/kurtosis.

Missing Data. If participants were missing data for some items within in a scale, these were imputed using the “mean of nearby points” method in SPSS. This method of imputation takes the average of up to two nearby points in the scale to calculate a value for missing data.

Drop-Outs. Drop-outs were defined as those participants who informed IIT research staff that they no longer wanted to participate in the intervention before the end of the 8-month period. Participants who dropped out of the BHL or BHL+PHN interventions were not omitted from the dataset unless they did not complete any survey assessments after the initial interview. In other words, if at least one additional survey assessment was completed following baseline, missing data was imputed as described above.

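### The 81% power figure is a pre-study MPLUS result for weight at N=210; no power is reported for the two-timepoint 3x2 ANOVA that replaced the planned analysis, and the stated inputs do not fix it

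*Combined protocol and SAP*

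**What the plan says.** The power paragraph of the Statistical Analysis Plan gives method and timing: "A power analysis was carried out prior to the beginning of the study in MPLUS using the Saris and Satorra (1993) method". It gives the assumed effects: "an effect size (standardized weight change) of -.07 in the BHL condition and -.20 in the BHL+PHN condition was expected". It then states the result: "A sample size of 210 has 81% power to detect group differences". Recruitment gives the same target, "or 70 per condition".

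The opening paragraph of the SAP describes a later change made because of missing data: the "data analysis plan was revised from 3x4 and 3x13 ANOVAs to 3x2 ANOVAs", using baseline and 8 months only, for all intent-to-treat analyses. The reasons given are "minimizing missing data, retaining power, maintaining intended plans to observe interventions from pre-test to post-test".

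The SAP does not state alpha, the MPLUS model, the SD used to standardize the effects, the assumed baseline to 8-month correlation, the contrast to which the 81% applies, an allowance for dropout, or the number analysed. It gives no power figure for the 3x2 ANOVA.

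**The concern.** The only power figure predates the analysis now described and was obtained by a model-based method. With two timepoints, the group-by-time test is a one-way ANOVA on change scores, so its power is governed by the SD of change. That quantity cannot be recovered from what the SAP states.

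A reader who meets a null 3x2 result next to the 81% will tend to treat it as a negative finding from a well-powered comparison. Whether that is fair depends on assumptions that are not written down. The effects also concern weight only, whereas the 3x2 ANOVA serves all intent-to-treat analyses, and the assessments described in the protocol include self-reported physical and mental health outcomes and the Healthy Lifestyle Behaviors score.

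**Working it through.** **Inputs from the documents.** N=210, 70 per arm; effects -.07 (BHL) and -.20 (BHL+PHN); stated power 81%.

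**Assumptions.** IC-TAU change 0; two-sided alpha .05; 70 analysed per arm; equal SDs at baseline and 8 months; r = baseline to 8-month correlation.

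**Reproducing the 81%.** The inputs alone do not reproduce it, because the model, alpha and standardizer are missing. It can be reached by adding assumptions. For example, treat the two effects as standardized path coefficients of uncorrelated predictors. Then R² = .07² + .20² = .0449, λ = 210 × .0449/.9551 = 9.87, and a 2-df chi-square test has 81.0% power. With the -.5 correlation that equal-arm dummy variables have, R² = .0449 - 2(.07)(.20)(.5) = .0309, λ = 6.70, and power is 63%. The documents do not say whether either was the model used.

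**Power of the 3x2 group-by-time test.**

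1. Mean of the three changes: (0 - .07 - .20)/3 = -.09.
2. Sum of squared deviations: .09² + .02² + .11² = .0081 + .0004 + .0121 = .0206.
3. Noncentrality: λ = 70 × .0206/SD² = 1.442/SD², where SD is the SD of change. The test is F on 2 and 207 df.
4. Effects in SD-of-change units: SD = 1 and λ = 1.442. Overall power is 17%, and 22% for BHL+PHN vs IC-TAU. No value of r alters this.
5. Effects in baseline-SD units: SD = √(2(1 - r)).

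| r | SD of change | λ | Overall power | BHL+PHN vs IC-TAU |
|---|---|---|---|---|
| .5 | 1.000 | 1.44 | 17% | 22% |
| .7 | .775 | 2.40 | 26% | 33% |
| .8 | .632 | 3.61 | 37% | 46% |
| .9 | .447 | 7.21 | 66% | 75% |
| .93 | .374 | 10.30 | 82% | 88% |
| .95 | .316 | 14.42 | 93% | 96% |

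On this reading, overall power of 81% needs SD of change .379, that is r = 1 - .379²/2 = .928. The BHL+PHN vs IC-TAU contrast alone needs r of about .91.

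**Other contrasts.** At r=.93, where overall power is 82%, BHL+PHN vs BHL (difference .13) has about 53% power and BHL vs IC-TAU (difference .07) about 20%.

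**Fewer analysed.** No analysed N is given, so these values are illustrative. At r=.93, overall power is 72% with 56 per arm (168) and 59% with 42 per arm (126). The r needed for 81% rises to .943 and .957.

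**The case against.** The strongest reply is that the 81% may have been sound, and that power for weight may still be high. Body weight could be a stable measure, and nothing in the documents excludes r above .93, where overall power exceeds 81%. Other readings also reach or approach the figure with a lower r: a four-wave linear slope with the effect attained at 8 months needs r=.82, and per-wave effects doubled by 8 months give 79% at r=.7. This stands. A reader might infer from the lower rows of the table that the trial was underpowered for weight, or that the 81% was miscalculated. The documents support neither inference, because they do not say which row or which standardizer applies. The alternative readings do not rescue the figure for the current test either: the four-wave slope is not the 3x2 ANOVA, and the per-wave reading needs an effect definition that the SAP does not give.

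Second, the power statement in "minimizing missing data, retaining power, maintaining intended plans to observe interventions from pre-test to post-test" is most naturally relative: with two timepoints, fewer participants are lost for an incomplete record than with four or thirteen. That rationale is reasonable, but the SAP neither limits the claim to that comparison nor puts a figure on it.

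Third, a reader might infer that power was never recalculated. The documents show only that no recalculation is reported. They do date the 81% correctly and never assign it to the 3x2 ANOVA in so many words. It is nevertheless the only power figure beside that analysis.

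Fourth, the SAP describes its analyses in the past tense, so a new calculation cannot change the sample size. That is true. The correction bears on how the results are read.

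**Conclusion.** The point holds as a gap between a stated figure and the analysis it accompanies. The 81% belongs to a pre-study MPLUS calculation for weight at N=210. It cannot be attributed to the 3x2 group-by-time test, to an analysed sample below 210, or to outcomes other than weight.

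The size of the gap is undetermined. Under the assumptions listed, overall power for the 3x2 test is 17% in SD-of-change units. In baseline-SD units it runs from 17% at r=.5 to 93% at r=.95, passing 81% at about r=.93. That threshold exists only for baseline-SD units, 70 analysed per arm, no IC-TAU change and two-sided .05, and the SAP states none of these as the basis of its figure.

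The missing-data rationale for the revision makes the analysed N material. The Drop-Outs section also allows it to fall below the number enrolled, since it omits intervention drop-outs with no assessment after baseline.

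**What to change.** - In the power paragraph, label the 81% as the pre-study MPLUS figure for weight at N=210.
- For the current analysis, give instead the power of the 3x2 group-by-time test at the analysed N. State alpha, the standardizer and the assumed baseline to 8-month correlation, with a short table over r, and say that it applies to weight.
- In the opening SAP paragraph, limit the claim about power to a comparison with complete-case 3x4 and 3x13 ANOVAs.
- Report each arm contrast with its confidence interval, so that a null result is judged by its precision and not by the 81%.

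The cost is SAP wording, one small table and intervals from data already collected, with no new participants. The downside is that the stated power may become less favourable.

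### The 81% power is stated for 210 participants, which is also the recruitment target, with no stated allowance for attrition, although the plan reports missing data and omits some drop-outs

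*Combined protocol and SAP*

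**What the plan says.** The Recruitment section states: "The target sample size for this study was 210 African Americans with serious mental illness and weight concerns (or 70 per condition").

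The power paragraph of the Statistical Analysis Plan states: "A power analysis was carried out prior to the beginning of the study in MPLUS using the Saris and Satorra (1993) method". It gives the assumed effects ("an effect size (standardized weight change) of -.07 in the BHL condition and -.20 in the BHL+PHN condition was expected") and concludes: "A sample size of 210 has 81% power to detect group differences". Alpha, the variances, the correlation between timepoints, the fitted model and any missing-data assumption are not given.

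The opening of the Statistical Analysis Plan states: "Due to missing data, data analysis plan was revised from 3x4 and 3x13 ANOVAs to 3x2 ANOVAs". The new analysis compares the three groups at baseline and 8 months. Keeping power is given as one reason for the revision, but no power figure is given for the revised test.

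Under Drop-Outs, participants who left either intervention "were not omitted from the dataset unless they did not complete any survey assessments after the initial interview". For the others, "if at least one additional survey assessment was completed following baseline, missing data was imputed as described above". The only method described above that sentence is the one under Missing Data, for items missing within a scale: "This method of imputation takes the average of up to two nearby points in the scale to calculate a value for missing data".

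**The concern.** The number that yields 81% and the number to be recruited are the same, so on its face the plan adds nothing for loss to follow-up. A pre-post ANOVA needs an 8-month value for each person it analyses. The plan records that data were missing, and it removes at least one class of participant from the dataset.

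What is at stake is how a null result is read. The 81% is the only power figure in the documents. A reader of a non-significant 3x2 result may credit it with 81% power when it came from a smaller or partly imputed sample.

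**Working it through.** **Inputs.** From the documents: N = 210, 70 per arm, stated power 81%, standardized effects -.07 (BHL) and -.20 (BHL+PHN). Assumed, because not stated: two-sided alpha .05, zero effect in IC-TAU, SD of 1, loss spread evenly over the arms, and loss rates of 5% to 40%.

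**Step 1: can the 81% be reproduced?** Not from what is given. With group means 0, -.07 and -.20, the overall mean is -.09 and the between-group variance is (.09² + .02² + .11²)/3 = .0206/3 = .00687. The noncentrality is λ = 210 × .00687 = 1.44, and the overall F test on 2 and 207 df has 17% power. For a change score, λ is multiplied by 1/[2(1 − ρ)], where ρ is the baseline to 8-month correlation:

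- ρ = .7: λ = 2.40, power 26%
- ρ = .9: λ = 7.21, power 66%
- ρ = .95: λ = 14.42, power 93%

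Power reaches 81% at ρ of about .93. The stated figure is therefore attainable under unstated inputs and is not shown to be wrong. It is taken as given below.

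**Step 2: what does loss do to it?** Solving for the noncentrality that gives 81% at N = 210 yields λ = 10.01 for the 2-df overall F test and 8.13 for a 1-df contrast. With the effect held fixed, λ is proportional to the number analysed: λ(n) = λ(210) × n/210. For n = 168, λ = 10.01 × 168/210 = 8.01.

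| Assumed loss | n | λ (2 df) | Power, overall test | Power, 1-df contrast |
|---|---|---|---|---|
| 0% | 210 | 10.01 | 81% | 81% |
| 5% | 200 | 9.54 | 79% | 79% |
| 10% | 189 | 9.01 | 76% | 77% |
| 20% | 168 | 8.01 | 71% | 72% |
| 30% | 147 | 7.01 | 65% | 66% |
| 40% | 126 | 6.01 | 57% | 59% |

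Power is about 80% at n = 205, so the margin over 80% is about five participants. Power is five points down at a loss of about 11% for the overall test (.11 × 210 ≈ 23 people) and just under 12% for the contrast. Loss below about 5% costs roughly two points or less.

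**Step 3: who counts as lost?** The text separates three groups.

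- *Intervention drop-outs with no survey after baseline.* They are omitted, and each one lowers the analysed number.
- *Intervention drop-outs with a 4- or 12-month survey but no 8-month assessment.* They are kept, and their missing data are imputed. The method cited averages neighbouring points within a scale. When the whole assessment is absent, that scale has no neighbouring 8-month items to average. How a value is produced is not stated, and a singly imputed value does not supply the information of an observed one.
- *IC-TAU participants, and anyone lost without telling staff.* A drop-out is defined as someone who told staff they no longer wanted the intervention, so no rule is stated for these people.

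In the table, loss means participants who contribute no observed 8-month value. If only the first group is counted, the same table applies with a smaller percentage.

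**The case against.** A reader might infer that everyone without an 8-month value is dropped, or that 210 can be analysed only if every recruit completes that assessment. The documents do not support this. The Drop-Outs paragraph keeps intervention drop-outs who have at least one later survey, so a missing 8-month assessment alone is not a stated reason for exclusion. The omitted group may be much smaller than the group without 8-month data.

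Four further points can be made for the plan:

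- The move to a 3x2 analysis was itself a response to missing data. The original designs needed data at 4 or 13 occasions, so abandoning them does not show how many 8-month values were missing. This stands: nothing in the documents places the trial in the 20% to 40% rows.
- The 210 is a target. The numbers enrolled and analysed are not reported. This also stands, and it means a shortfall is possible but not demonstrated.
- The Mplus model may have allowed for missing data. It may have, but the documents do not say so, and one sentence would settle it.
- The 81% predates the 3x2 revision and cannot be rebuilt, so values scaled from it are only as good as that anchor. This stands, and it is why they are not offered as corrected power.

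None of this removes the core point. Even on the most generous reading, some participants are omitted, the powered number equals the recruitment target, and no allowance is stated.

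**Conclusion.** The point holds in a limited form. The 81% is tied to 210 participants with no stated attrition allowance, and the written rules deliver 210 from 210 enrolled only if nobody falls under the omission rule. Those kept by imputation do not fully make up the difference.

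The size cannot be fixed, because no loss rate is reported. It runs from about two points of power at 5% loss to about ten at 20% and sixteen at 30%. Those figures rest on an alpha of .05, an 81% anchor accepted without verification and applied to the 3x2 test, and even loss across arms.

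The documents do not show that the 81% was miscalculated or that the analysed set was badly underpowered. This is a reporting weakness that should be corrected because it affects how null results are read.

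**What to change.** 1. Reword the power sentence to say that 81% is the pre-study figure for 210 analysable participants with no stated attrition allowance. If the Mplus model had an allowance, state it.
2. Beside each 3x2 result, report the number per arm with observed baseline and observed 8-month values, apart from any imputed values.
3. Restate power at that number, with alpha, the test and the other assumptions.
4. Do not cite 81% when interpreting null results.

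The cost is a few sentences, a count per arm from data already held, and one recalculation. The stated power is likely to become less favourable. No new data or extra enrolment is proposed.
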